1.9 Data Collection

A. Primary Data Collection- N/A

B. Secondary Data Collection – N/A

1.10 Timetable/Schedule of Events

Upon IRB approval-Sept. 2023 Collection of blood and fecal specimens.

Sept. 2021-Sept. 2023 Analysis of blood and fecal specimens.

Sept. 2021-Aug. 2023 Fecal transplantation in germ free mice and analysis for EAE.

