We will establish a germfree 3A6/DR2a at Taconic Inc. and expand them in our facility. Since 3A6/DR2a mice are prone to develop EAE between the age of 6 to 10 week-old, 4 week-old mice will be used for creating HMA-3A6/DR2a mice. Fecal samples will be collected from HDs and MS patients on regular diet and HFS at 3 time points (pre-treatment; 8, and 12 weeks after treatment) and the fecal sample will be transplanted into 3A6/DR2a mice (20 mice in each group). Each fecal sample (0.5 g) will be diluted in 25 mL of a sterile Ringer working buffer in an anaerobic chamber. The fecal material will allowed to settle by gravity and the clarified supernatant will be mixed with an equal volume of 20% (w/v) skimmed milk (Oxoid). Mice will be orally administered with 100 μ L of fecal suspension inoculum. The development of spontaneous EAE will be monitored until the age of 20 weeks.

We will also assess the microbial composition and intestinal permeability in the transplanted mice. The fecal samples will be collected every 7 days post fecal transplantation and gut microbiota composition will be examined by sequencing of V4 region of 16S rRNA gene using iontorrent sequencer (Thermofisher) as described earlier. To measure the intestinal permeability, the transplanted mice will be administered with 150 μ l of FITC dextran by oral gavage and appearance of FITC-dextran in the blood will be measured 4 h after oral inoculation. The serum FITC-dextran concentration will be measured using a fluorimeter. Since serum levels of endotoxin is also a biomarker of intestinal permeability, serum endotoxin activity will be measured using PierceTM Limulus Amebocyte Lysate (LAL) Chromogenic Endotoxin Quantitation Kit.

We will next assess the development of pathogenic and regulatory immune cells. Three mice in each group will be euthanized at the age of 6-10 week-old and development of pathogenic Th1, Th17, and Th-GMCSF cells in intestinal lamina propria, mesenteric lymph nodes, spleen, and CNS will be examined by flow cytometry with anti-CD4, V β 5.1, CD3, IFN- γ , IL-17A, GM-CSF mAbs. Development of Foxp3 Tregs will be examined by flow cytometry with anti-Foxp3, GITR, CD4, and V β 5.1 mAbs. Based on our earlier findings (19), down-regulation of E3 ubiquitin ligase, CBLB and ITCH, will be examined by q-PCR.

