We will also examine the development of inducible EAE in C57BL/6 mice transplanted with fecal samples. Germ-free C57BL/6 mice will be purchased from Taconic Inc. and expanded for the experiment. The fecal samples will be collected from regular diet- and HFS-treated HDs and MS patients as described above and transplanted into the germ-free C57BL/6 mice (10 in each group). The transplanted mice (7-9 week-old) will be immunized with MOG35-55 at 200 ug/mouse and injection with pertussis toxin at 100 ng/mouse. Development of EAE will be examined for 40 days. Demyelination and axonal loss in the brain and spinal cord will be examined by immunohistology

with anti-MBP and -Neurofilament Abs, respectively. Microbial composition, intestinal permeability, and development of Th-1, Th-17, Th-GMCSF and Foxp3 Tregs will be examined as described above.

3. Explore biomarkers of MS-associated gut dysbiosis and response to HFS:

RR-MS and healthy donors (21-55 year-old) from RWJ MS Centers will be asked to participate in this study according to institutional IRB guidelines. In this study, fecal and blood samples will be collected from RR-MS patients during relapse (before steroid treatment) and later during remission and examined for intestinal inflammation, permeability and microbial composition. We will enroll 25 patients based on sample size calculation using related previous studies with a statistical power of 80% (8, 20). The fecal samples (200 mg) will be dissolved in 0.5 ml PBS containing proteinase inhibitor and the supernatant will be collected. The concentration of intestinal inflammation biomarkers including Lcn-2, Calprotectin, and Lactoferrin, and a biomarker for intestinal permeability, serum zonulin, will be measured by ELISA assay. We will examine the association between increase in intestinal inflammation/permeability and disease activation.

The fecal samples collected from HFS-treated and un-treated MS patients at the 3 time points described in Aim-1, will be analyzed for intestinal inflammation and permeability as described above. We will simultaneously examine the microbial composition in the fecal samples as described in Aim-1 to determine if an association between MS relapse and gut dysbiosis exists.

C. Study Duration

Subjects participation will be 12-week period.

Study Timetable:

Upon IRB approval-Sept. 2023 Collection of blood and fecal specimens

Sept. 2021-Sept. 2023 Analysis of blood and fecal specimens

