4.3 Number of Subjects

A. Total Number of Subjects

50 MS patients and 50 healthy donors will be enrolled in this study. Please refer to section “1.5 Sample Size Justification” for calculation regarding sample size.

B. Total Number of Subjects If Multicenter Study – N/A

C. Feasibility

RWJ MS Center evaluates enough newly diagnosed MS patients every year to be able to recruit 50 MS patients for the study over 1 years. 50 healthy volunteers will be recruited from Rutgers students/staff and New Jersey local resident..

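### The mouse timetable closes before the last stools could be followed to 20 weeks of age, and nothing keeps a donor's before and after stools in one mouse cohort

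*Combined protocol and SAP*

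**What the plan says.** The timetable appears twice, in section 1.3 C and section 1.10, with the same dates. Specimens: "Upon IRB approval-Sept. 2023 Collection of blood and fecal specimens". Mouse work: "Sept. 2021-Aug. 2023 Fecal transplantation in germ free mice and analysis for EAE". The IRB approval date is not given.

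Section 1.3 B.2 describes two mouse models.

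- **Spontaneous model (3A6/DR2a).** Age at transfer: "4 week-old mice will be used for creating HMA-3A6/DR2a mice". Follow-up: "The development of spontaneous EAE will be monitored until the age of 20 weeks". Stools used: "3 time points (pre-treatment; 8, and 12 weeks after treatment) and the fecal sample will be transplanted into 3A6/DR2a mice (20 mice in each group".
- **Induced model (C57BL/6).** Mice are immunised at 7 to 9 weeks of age, and then "Development of EAE will be examined for 40 days".

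Section 1.6 defines Experiment 2 by four groups (healthy donors and MS patients, with and without HFS), with EAE incidence and severity as outcomes. Section 1.8 keeps specimens at -80 °C for 3 years. Section 4.3 expects the centre "to be able to recruit 50 MS patients for the study over 1 years"; it gives no recruitment period for healthy volunteers.

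No section sets a last stool date for the mouse work, says that a donor's stools are held and transferred together, or says how litters and calendar cohorts are balanced over time points. Section 6.1 (Data Analysis) has no text beneath its heading in the copy reviewed.

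**The concern.** There are two linked problems.

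First, the dates conflict with the stated follow-up. The mouse work ends before stool collection does, and the real shortfall is longer than that one calendar month because each 3A6/DR2a transfer occupies 16 weeks. Any shortfall falls first on the Week 12 stool, then on the Week 8 stool, and last on the baseline stool.

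Second, transfer is scheduled alongside collection. If stools are transferred as they arrive, a donor's baseline and later stools go into animals born at different times. A difference in EAE between them would then combine any effect of HFS with any difference between mouse cohorts. Once a baseline stool has been transferred on its own, the analysis cannot separate the two for that donor.

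**Working it through.** The check is calendar arithmetic. Only months are given, so the first and last day of each month are both tried. Transfer is assumed to take place on the day the stool is passed, which is the most favourable case.

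**Follow-up per 3A6/DR2a transfer.** 20 - 4 = 16 weeks = 112 days.

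**Last transfer that can finish** = mouse end date - 112 days.

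| Mouse work ends | Last transfer | Latest baseline for a Week 12 stool (-84 days) | Latest baseline for a Week 8 stool (-56 days) |
|---|---|---|---|
| 1 Aug 2023 | 11 Apr 2023 | 17 Jan 2023 | 14 Feb 2023 |
| 31 Aug 2023 | 11 May 2023 | 16 Feb 2023 | 16 Mar 2023 |

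**Uncovered calendar time.** The shortest gap is 11 May to 1 September 2023: 113 days, about 16 weeks. The longest is 11 April to 30 September 2023: 172 days, about 25 weeks.

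**Mouse end date needed if collection is used to its end.** 1 September 2023 + 112 days = 22 December 2023; 30 September 2023 + 112 days = 20 January 2024.

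**Induced model.** The last immunisation allowing 40 days is 22 June 2023 (end 1 August) or 22 July 2023 (end 31 August). This model is less tight, but it does not reach September either.

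**Share of Week 12 stools that come too late.** The last baseline whose Week 12 stool falls by 30 September 2023 is 84 days earlier, 8 July 2023. With mouse work to 31 August, late baselines are those from 16 February to 8 July 2023, which is 142 days. Accrual is assumed even in each case.

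- One-year accrual ending 8 July 2023: 142 / 365 = 39%. If the mouse work ends on 1 August the late interval is 172 days and the share is 172 / 365 = 47%.
- Accrual from 1 September 2021 to 8 July 2023 (675 days): 142 / 675 = 21%.
- One-year accrual starting by 17 January 2022 (end 1 August) or 16 February 2022 (end 31 August): 0%, because every Week 12 stool arrives by the last transfer date.

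**Cohort separation.** Mice aged 4 weeks when a donor gives the baseline stool are 4 + 8 = 12 weeks old at Week 8 and 4 + 12 = 16 weeks old at Week 12. Since recipients must be 4 weeks old, stools transferred on arrival necessarily go into different cohorts. They share a cohort only if the earlier stools are stored, which the plan allows but does not require.

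**The case against.** A reader might infer that post-HFS stools will certainly be lost, with late donors feeding only the before side. The documents do not support that. Section 4.3 gives one year for recruiting MS patients, and an early enough start leaves no scheduled MS stool late. The last collection months may also serve Group E: section 1.8 allows relapse sampling after study completion and a recovery sample 1 to 6 months later, and Experiment 2 does not use that group. Nor does the plan say that every donor's stool is transferred. With 25 donors per arm and 20 or 10 mice per group it may pool or select, and it could drop incomplete sets.

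A reader might also infer that Experiment 2 as a whole is confounded. That goes too far. Untreated Groups B and D give stool at the same three time points. If arms are enrolled concurrently, cohort drift acts on HFS and non-HFS transfers alike, so the between-group contrast is partly protected. The evidence in section 1.4 that EAE depends on microbial status comes from conventionally housed or antibiotic-treated mice, not germ-free recipients, and no drift figure is given.

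Finally, the plan describes 3A6/DR2a mice as "prone to develop EAE between the age of 6 to 10 week-old". Transfers up to about 20 June to 20 July 2023 (end date - 42 days) would cover that window.

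These points limit the size of the problem. They do not remove the conflict between the stated dates and the stated 20 weeks, or supply a batching rule.

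**Conclusion.** The point holds in a limited form. On the plan's own dates, 3A6/DR2a transfers after about 11 April to 11 May 2023 cannot reach 20 weeks of age, and a stool passed in September 2023 arrives after the mouse work has closed. The share of scheduled Week 12 stools affected cannot be settled without the IRB approval and accrual dates: from none to about 39% if mouse work runs to 31 August, with even accrual and same-day transfer assumed. The number of affected mice cannot be computed, because the plan does not say how stools are assigned to animals.

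The cohort problem is a possibility left open by the plan, not a certainty. It bears mainly on the within-donor before/after contrast.

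Priority: consider. Section 1.3 D lists no mouse outcome among the primary or secondary endpoints, and no human outcome is affected. The change is still worthwhile, because it is cheap beforehand and cannot be made afterwards.

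**What to change.** 1. **Sections 1.3 C and 1.10.** Either set a last-stool date for Experiment 2 at least 16 weeks before the mouse end date and use only donors with complete stool sets, or move the mouse end date to about 16 weeks after the last Experiment 2 stool (about January 2024 if that stool is passed at the end of September 2023). State end dates by day. Sixteen weeks also covers the induced model: immunisation at 9 weeks of age at the latest plus 40 days is 63 + 40 = 103 days, below 112 even if counted from birth.
2. **Section 1.3 B.2.** For each donor used, freeze the baseline, Week 8 and Week 12 stools at -80 °C in the same way. Freezing only the earlier ones would tie freezing to time point. Transfer all three in the same week into littermates randomised among that donor's stools. Include HFS and non-HFS donors in every mouse cohort.
3. **Section 6.1.** Enter mouse cohort as a block in the analysis of EAE incidence and severity.

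Cost: some protocol wording and use of storage already planned. Some late donors go unused, or the mouse work ends about 5 months later. All inocula are frozen rather than fresh, which should be stated as a limitation.

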2.2 Research Staff Training

All study staff participants are familiar with research protocol, study procedures and maintaining subject confidentiality. They have each reviewed the research protocol and are familiar with study procedures due to experience from previous studies.

2.3 Resources Available

For study related purposes, the Department of Neurology, has medical resources available to collect the specimens, research laboratory to process the specimens, and animal facility to transplant the human fecal specimens to mice.

Research laboratory to process fecal sample and perform next-generation sequencing for gut microbiota profiling is available at Department of Biochemistry and Microbiology.

3.0 Multi-Center Research

N/A

4.0 Subject Considerations

4.1 Subject Selection and Enrollment Considerations

A. Method to Identify Potential Subjects

2017 McDonald criteria will be used to select relapsing remitting MS patients. Age and sex matched healthy donors will be recruited from Rutgers students/staff volunteers or New Jersey local resident using e-mail with study flyers.

B. Recruitment Details

The study will recruit both participants who have MS and Healthy Volunteers. Subjects will be recruited at RWJ Center for Multiple Sclerosis ambulatory clinic.

Patients will be recruited from the outpatient neurology clinic of the Rutgers Robert Wood Johnson Center for MS. The patients will be asked to participate in the study during their regular clinical visit to RWJ MS Center. Only if the patient agrees to participate and meets enrollment criteria will they be enrolled in the study.

Healthy volunteers will be recruited from Rutgers students/staff volunteers or New Jersey local resident. There will be no undue influence on students / staff. Participation is completely voluntary. The healthy donor recruitment flyer will be emailed to students / staff. Those who are interested can reach out to obtain further information and be screened for eligibility.

C. Subject Screening

Subjects will be screened by [name] at RWJ MS center based on inclusion and exclusion criteria laid out in this study.

▪ Inclusion Criteria

1. Patients who meet 2017 McDonald criteria for RRMS.
2. Both males and females (age 21-65 year old).
3. Newly diagnosed and RRMS patients who are taking non-oral MS medications like interferon, Copaxone and Tysabri.
4. RRMS patients who refuse to take MS medications but are interested in other interventions.
5. Healthy volunteers without any chronic inflammatory or autoimmune diseases will be included in the study as controls.

Exclusion Criteria

1. Primary or secondary progressive MS.
2. Patients with autoimmune comorbidities.
3. Having received prior chemotherapy.
6. Pregnant women.
7. Cognitively impaired.
8. Antibiotic use within last 6 months.
9. Probiotic use within the last 2 months.

10. Self-reported allergy or intolerance to any ingredients in the fiber supplement.
110. Self-reported or diagnosed gastrointestinal disorders (such as; Irritable Bowel Syndrome, Diverticulitis, Chron's Disease)
121. Active or history of malignant tumors

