1.3 Research Design and Methods

RR-MS patients will be recruited from the Robert Wood Johnson Center for MS under the direction of [name]. The patients will be asked to participate in the study during their regular clinical visit to the MS Center.

Inclusion criteria includes patients aged 21-65 Relapsing Remitting Multiple Sclerosis (RRMS) who met the 2017 McDonald criteria.

The first group (**Group A**) of MS patients (**n=25**) will receive a dietary fiber supplementation. They will consume 60 g/day of HFS for 12 weeks (High-fiber supplement group, Group-A). The supplement consists of a mixture of soluble fibers (from inulin and fibersol-2) and insoluble fibers (from oat bran, corn bran, wheat bran and sorghum bran) and it will be consumed as a drink.

The second group of MS patients (**Group B**) (**n=25**) will not consume any high fiber supplement.

The first group (**Group C**) of healthy volunteers (**n=25**) will receive a dietary fiber supplementation. They will consume 60 g/day of HFS for 12 weeks. Healthy volunteers will not have MS.

The second group (**Group D**) of healthy volunteers (**n=25**) will not consume any high fiber supplement.

For Groups A, B, C & D stool, and serum samples will be collected at 3 time points (baseline; Week 8; & Week 12).

Group E (n=25) will consist of 25 subjects with MS who experience an MS flare up.

These 25 subjects can be those participants with MS who are already part of the above study (Group A or B) and consent to 2 extra blood and 2 extra fecal samples collected at the time of the acute flare up and upon resolution of symptoms.

Screening visits will typically take place during routine MS follow up visit at the Robert Wood Johnson Center for MS. During this time, eligibility will be reviewed, and consent will be obtained once the patient has had time to review the study, have questions answered, and agree to participate. During this screening visit, details regarding the patients MS history, food allergies/intolerances, medical history, and medications will be recorded. Eligible participants will be asked to provide blood and stool samples for baseline assessment.

A. Research Procedures

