These 25 subjects will be those participants with MS who are already part of the above study (Group A or B) and consent to 2 extra blood and 2 extra fecal samples collected at the time of the acute flare up and upon resolution of symptoms. These subjects will be asked to sign a separate consent form agreeing to be part of the MS flare up group (n=25). Since around 50% of RRMS patients relapse at least once per year, we anticipate recruiting 25 relapsing RRMS patients from Group A and B in 1 years (2). RRMS flare up and resolution will be determined by [name].

Table-1. Schedule of specimen collection

Screening/Baseline assessment	8 weeks post HFS	12 weeks post HFS	Unscheduled visit at MS Relapse	Unscheduled visit at MS remission
MS history Medical history Medication history Food Allergy Consent Blood draw* Fecal collection*	Blood draw Fecal collection	Blood draw Fecal collection	Blood draw** Fecal collection**	Blood draw Fecal collection

--	--	--	--

*Sample collection will be done on the day of screening or before high fiber supplement.

** Sample collection will be done at MS relapse before steroid treatment.

Sample collection:

1. Stool Sample: Subjects will be asked to collect a single-stool sample without any laxative or dietary restrictions using a sample collection kit (Appendix 1). The collected stool sample will be brought to the MS research laboratory by the participants. If participants cannot bring the stool sample to the MS research laboratory, our lab staff will pick up the stool sample. The stool sample will be examined for the composition of gut bacteria. The stool sample will also be transplanted into an animal model of MS and examined for the development of experimental autoimmune encephalomyelitis (EAE).

2. Blood Draw: All participants will visit RWJ MS center to provide a blood specimen. Each subject will have a blood draw (80ml – about 5 tablespoons) as shown in Table-1. The immune cells will be isolated from each blood specimen and the presence of pathogenic and regulatory immune cells will be analyzed.

*NOTE: It is requested that all blood work be fasting. Nothing to eat or drink 10-12 hours before blood draw. Subjects may have water &/or black coffee /tea.

Fasting is very important to check the levels of short-chain fatty acid in the serum.

B. Experiment

1. Examine the effect of HFS on production of SCFA, intestinal microbial composition, and intestinal permeability

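### Entry criteria set look-back windows for antibiotics and probiotics but print none for recent relapse, steroids or a new MS drug, so baseline drift may be read as an HFS effect

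*Combined protocol and SAP*

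**What the plan says.** Section 4.1 C (inclusion criteria) admits "Newly diagnosed and RRMS patients who are taking non-oral MS medications like interferon, Copaxone and Tysabri" and also "RRMS patients who refuse to take MS medications but are interested in other interventions". The exclusion list has two look-back windows for recent exposures: "Antibiotic use within last 6 months" and "Probiotic use within the last 2 months". No printed criterion sets a time since the last relapse, a time since systemic steroids, or a minimum time on (or off) an MS drug. The exclusion numbering passes from 3 to 6, and items 4 and 5 do not appear in the text as read.

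Section 4.3 C gives the basis for recruitment: "RWJ MS Center evaluates enough newly diagnosed MS patients every year to be able to recruit 50 MS patients for the study over 1 years".

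Section 1.3 says that at screening "food allergies/intolerances, medical history, and medications will be recorded" along with MS history, but no entry rule uses this information. Table-1 in section 1.3 A puts screening and baseline in one column, and its footnote allows the baseline sample on the screening day. The only rule on steroid timing concerns the relapse sample: "Sample collection will be done at MS relapse before steroid treatment".

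Section 1.3 D words the primary endpoint as a comparison of before with after HFS in 25 MS patients. It covers microbial composition, permeability, SCFA and immune cells. Section 6.1 (Data Analysis) is a heading with no text under it.

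**The concern.** A newly diagnosed patient may be close to a presenting attack, to its treatment, or to a first MS drug. Followed as written, the plan would let such a patient be consented and sampled at the same visit. Values at weeks 8 and 12 may then differ from baseline because of recovery, steroid wash-off or drug onset. In Group A a before-after comparison cannot separate that change from an HFS response.

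The plan's own rules suggest that these states matter. It keeps recent antibiotics and probiotics away from baseline, and it keeps steroids away from the relapse sample. Section 1.8 A places the post-relapse recovery sample 1 to 6 months after the attack, a span that includes the 8- and 12-week visits. Someone enrolled soon after an attack could thus pass, during HFS, through the same relapse-to-remission interval that Group E is set up to study.

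**Working it through.** **Is there a rule elsewhere?** Steroids appear in sections 1.3 A and 1.3 B only as a timing rule for relapse samples. Medication and MS history are recorded at screening, but nothing is conditional on them. No other section contains an entry rule on relapse, steroids or start of an MS drug.

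**The plan's own figure.** Section 1.5 reports n=20 per group at 5% type I error and 80% power, with 25 enrolled. It prints no mean difference and no SD, so the figure cannot be reproduced forward. Solved backwards (two-sided, normal approximation), n=20 per group corresponds to a standardised difference of (1.960 + 0.842) × √(2/20) = 0.886. This point does not dispute that figure.

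**Inputs for the size of the problem**
- n = 25 in Group A and 25 in Group B (section 1.3).
- 5% type I error (section 1.5); two-sided is assumed.
- Net drift δ, in SDs of the within-patient change. The documents give no value, so the range is an assumption: fraction affected × mean shift in those affected, with all shifts in the same direction. 20% × 0.5 SD = 0.1; 40% × 0.5 SD or 20% × 1.0 SD = 0.2; 40% × 1.0 SD = 0.4.

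**Before-after comparison in Group A, no HFS effect.** Paired t test, 24 degrees of freedom, critical value 2.064, noncentrality δ√25 = 5δ.

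| Net drift (SD) | Noncentrality | Chance of p<0.05 |
|---|---|---|
| 0 | 0 | 5.0% |
| 0.1 | 0.5 | 7.7% |
| 0.2 | 1.0 | 16.1% |
| 0.4 | 2.0 | 48.4% |

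The same test has 80% power at 0.584 SD, so these drifts are 0.1/0.584 = 17%, 34% and 68% of the detectable change.

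**Group A versus Group B, difference in change, no HFS effect.** Two-sample t test, 48 degrees of freedom, critical value 2.011. Only the difference in drift Δ between the groups enters: noncentrality Δ√(25/2) = 3.54Δ.

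| Difference in drift (SD) | Noncentrality | Chance of p<0.05 |
|---|---|---|
| 0 (shared drift) | 0 | 5.0% |
| 0.05 | 0.18 | 5.3% |
| 0.1 | 0.35 | 6.4% |
| 0.2 | 0.71 | 10.7% |
| 0.4 | 1.41 | 28.3% |

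A 10-percentage-point imbalance in affected patients, at 0.5 to 1.0 SD each, gives Δ = 0.05 to 0.1, hence 5.3% to 6.4%. If 30% of patients are affected and fall into the groups by chance, the groups differ by 5 or more such patients about 16% of the time. At 1.0 SD each, a gap of 5 is 5/25 × 1.0 = 0.2 SD, or 10.7%.

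**The case against.** The strongest reply is that Group B already deals with this. It consists of MS patients without HFS, sampled at the same three times, and section 1.6 defines Experiment 1 by four groups. Drift common to A and B cancels in that contrast. This stands, and it limits the point. A reader might infer that a small imbalance between A and B would do as much damage as drift does in the before-after test. The figures do not support that: at equal SD values the A-versus-B error is well below the before-after error. What remains is that section 1.3 D words the primary endpoint as before versus after. The plan also describes no random allocation, balancing or baseline adjustment that would make drift equal in A and B. Groups C and D are healthy and cannot show MS-specific drift.

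Second, 0.4 SD is a stacked case. Recovery, steroid wash-off and drug onset are different states, and nothing in the documents says that they move Tregs, Th1/Th17 cells, zonulin or Lcn-2 the same way; opposing shifts would partly cancel. If the SD is that of patients without drift, the mixture of affected and unaffected patients widens the spread to √(1 + 0.4 × 0.6) = 1.11 SD, and 48% becomes about 41%. This stands too: the documents support that values may drift, not that they will.

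Third, a reader might infer from objective 2 that the plan assumes its markers change with exacerbation. It does not. Section 1.2 makes that result conditional, and section 1.5 says there are no published intestinal-inflammation biomarker data in MS. The pre-steroid sampling rule is better evidence of what the plan considers disturbing, though it governs relapse samples only.

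Fourth, the missing exclusion items 4 and 5 limit certainty. They do not show that a rule existed, and no other section points to one.

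Finally, established treated patients and those refusing drugs are also eligible, so the newly diagnosed share is unknown.

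**Conclusion.** The point holds as a gap in eligibility that bears on the primary comparison. The printed criteria protect baseline from recent gut exposures but not from recent relapse, steroids or a new MS drug, while recruitment rests on patients in whom these are likely to be recent. The before-after endpoint cannot tell the resulting drift from an HFS effect.

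If net drift were 0.1, 0.2 or 0.4 SD of change, the false-positive rate of that comparison would be about 8%, 16% or 48%. For A versus B it stays at 5% under shared drift and is about 6%, 11% or 28% when drift differs by those amounts. The drift sizes and a common direction of shift are assumptions; the documents give neither. Confidence is moderate, because two exclusion items are not visible. The change should be made before enrolment, since an unstable baseline cannot be collected again.

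**What to change.** Add to section 4.1 C an entry-stability requirement for MS participants. It should cover time since last relapse, time since systemic steroids, and unchanged MS-drug status (including no drug) before the baseline sample. The investigators should set the intervals; the documents support no particular length.

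For patients who do not yet qualify, including those about to start an MS drug, defer the baseline sample and study entry, not MS treatment. Without the clause on planned starts, a stable untreated patient could begin a drug just after baseline and bring the same drift back in.

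Record the dates of last relapse, last steroid course and MS-drug start at screening, and compare Groups A and B on them. Base the HFS conclusion on the A-versus-B difference in change, and say so in sections 1.3 D and 6.1. That contrast removes shared drift, but it does not by itself remove imbalance while allocation is undescribed.

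The cost is a protocol amendment and three dates on the screening form. The real downside is delayed starts and somewhat slower recruitment of newly diagnosed patients against the one-year target in section 4.3 C.
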